5.7.2 Pharmacokinetic Parameters

Pharmacokinetic parameters will be derived for ibrexafungerp in plasma and in breast milk for participants in the PK population. Pharmacokinetic parameters are defined in [Table 3](#).

Table 3 : Pharmacokinetic Parameters

Parameter	Description
C_{\max}	Maximum concentration in plasma/breast milk
C_{\min}	Minimum concentration in breast milk
C_{av}	Average concentration in breast milk during the dosing

	interval
AUC ₀₋₂₄	Area under the plasma/breast milk concentration-time curve from time zero to 24 hours
M/P	AUC ₀₋₂₄ milk /AUC ₀₋₂₄ plasma
T _{max}	Time to reach maximum plasma/breast milk concentration
AUC _{0-t}	Area under the plasma/breast milk concentration from time zero to t _{last}
AUC _{0-inf}	Area under the plasma/breast milk concentration from time zero extrapolated to infinity
AUC%extrapolated	Percentage of AUC _{0-inf} due to extrapolation from t _{last} to infinity.
K _{el} or λ _z	Elimination rate constant in plasma
t _{1/2}	Elimination half-life in plasma
CL/F	Clearance or apparent oral clearance in plasma
V _d	Apparent volume of distribution in plasma

PK parameters will be presented by participant in data listings and will be summarized by participants in the PK population using descriptive statistics.

The PK parameters of ibrexafungerp will include maximum concentration (C_{max}) following first dose, area under the concentration-time curve (AUC₀₋₂₄) time to maximum concentration (T_{max}) after the first dose, and elimination half-life (t_{1/2}) after the second dose that will be calculated by means of noncompartmental analysis (NCA) using Phoenix WinNonlin Version 8.4 (Certara USA, Inc.). AUC₀₋₂₄ in milk to plasma ratio is of primary interest to the study objectives. In addition, since blood samples and breast milk will be collected to 108 hours, AUC_{0-t} and AUC_{0-inf} will also be calculated and presented.

Elimination rate constants and AUC determination will be based on the linear trapezoidal rule, and actual PK sample times will be used for the PK analyses. The t_{1/2}, if calculated, will use at least 3 time points from the logarithmic terminal phase portion of the concentration time curve. Pharmacokinetic parameters derived with Kel such as t_{1/2} and AUC_{0-inf}, will be listed but excluded from descriptive statistics if R² _adjusted < 0.8 in λz (Kel) estimation.

For determination of AUC_{0-inf}, if the percentage of extrapolated AUC is more than 20% of AUC_{0-inf} from t_{last} to infinity, then individual AUC_{0-inf} result will be listed but flagged as not reliable calculation. AUC_{0-inf} for these flagged subjects will not be included in descriptive statistics table.

The following plasma ibrexafungerp pharmacokinetic parameters will be calculated: area under the curve (AUC), peak plasma concentration (C_{max}), time to peak plasma concentration (T_{max}), plasma clearance or apparent oral clearance (CL/F), apparent volume of distribution (V_d), and terminal half-life (t_{1/2}).

The following PK parameters of ibrexafungerp in breast milk will be calculated: AUC

for the different collection periods, C_{av} based on AUC derived from collections at different time points above; total milk concentration data will be used to calculate C_{max} , C_{min} and T_{max} . The C_{av} is calculated as follows.

$$C_{av} = \text{AUC}_{0-24} / 24\text{h}$$

Plasma and breast milk PK parameters for individuals will be listed and summarized descriptively.

Plasma and breast milk concentrations and PK parameters will be summarized using descriptive statistics. Summary statistics for PK parameters except for T_{max} will be described by n, arithmetic mean (mean), arithmetic mean SD, arithmetic CV%, geometric mean, geometric SD, geometric CV%, min, median and max. For T_{max} , summary statistics will be described by n, median, min and max. For $t_{1/2}$, harmonic mean and pseudo SD will also be presented. CV% will be displayed in one decimal place.

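### SAP 5.7.2 gives Cmax and Tmax two different windows: no dose limit in Table 3, first dose in the derivation sentence, while Protocol 15.4 asks for them after the two-dose regimen

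*SAP*

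**What the plan says.** SAP 3.1 lists Cmax and Tmax among the primary endpoints for plasma and again for breast milk.

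SAP 5.7.2 then deals with them in three places:

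- **Opening and Table 3.** "Pharmacokinetic parameters will be derived for ibrexafungerp in plasma and in breast milk". The section refers to Table 3 for the definitions. Table 3 describes Cmax as "Maximum concentration in plasma/breast milk" and Tmax as "Time to reach maximum plasma/breast milk concentration". Neither entry names a dose or a time window.
- **Derivation sentence.** The sentence that names the noncompartmental method and the software says the parameters "will include maximum concentration (C_{max}) following first dose", then "time to maximum concentration (T_{max}) after the first dose", then "elimination half-life (t_{1/2}) after the second dose".
- **Closing lists.** One begins "The following plasma ibrexafungerp pharmacokinetic parameters will be calculated" and the other "The following PK parameters of ibrexafungerp in breast milk will be calculated". Both name Cmax and Tmax without a dose limit. The milk list says that total milk concentration data are the basis for Cmax, Cmin and Tmax.

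Protocol 15.4, with the same wording in the synopsis, asks for Cmax and Tmax after the VVC dosage regimen, in milk and in plasma. Protocol 9.1 describes that regimen as two doses on one day, 12 hours apart. The protocol has no first-dose restriction.

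**The concern.** The derivation sentence is the one a pharmacokinetic programmer would act on. It labels each parameter by dose: Cmax and Tmax with the first, half-life with the second. That looks like deliberate wording. It gives no reason for stopping at the first dose and does not say that it departs from the protocol.

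If it is followed, the reported Cmax and Tmax describe half of the regimen. With a half-life of 20-24 h and a second dose at 12 h, the regimen's peak is expected after the second dose. The parameter table would then give a peak that the same report's listings and 0-108 h plots exceed.

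Timing matters as well. The interim after five participants runs the full SAP analysis (SAP 5.9), and if the data are judged sufficient recruitment stops there. An unsettled window would be carried into what may be the final report.

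**Working it through.** The plan states no figure for Cmax, so there is none to reproduce. The check has two parts.

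**1. Text**

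| Place | Dose or time window for Cmax and Tmax | Matrix |
|---|---|---|
| SAP 5.7.2, Table 3 | none stated | plasma and milk |
| SAP 5.7.2, derivation sentence | first dose | not stated |
| SAP 5.7.2, closing lists | none stated | plasma; milk |
| Protocol 15.4 and synopsis | after the two-dose VVC regimen | plasma and milk |

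The second row is the one that does not fit.

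**2. Size, if the first-dose sentence is followed**

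Inputs from the documents:
- Single-dose Tmax 4 to 6 h; half-life about 20 h; exposure roughly dose-proportional, which supports superposition (Protocol 7.1).
- Half-life 24 h (Protocol 7.2).
- Plasma at 0, 2, 6, 8, 12 (before the second dose), 24, 36, 48, 72 and 108 h; milk intervals 0-2, 2-4, 4-8, 8-12, 12-18, 18-24, 24-36 h and later (SAP 4.5.1).

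Assumptions not in the documents: one compartment, first-order absorption, two equal doses adding linearly; for milk, concentration parallel to plasma and each collection equal to the mean over its interval.

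Formulas, in arbitrary units:
- k = ln 2 / half-life; ka solves ln(ka/k)/(ka − k) = Tmax
- c(t) = ka/(ka − k) × (e^(−kt) − e^(−ka·t)) for t ≥ 0, otherwise 0
- C(t) = c(t) + c(t − 12)

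Worked case, half-life 20 h and Tmax 5 h: k = 0.03466, ka = 0.607. The first-dose samples at 2, 6, 8 and 12 h are 0.675, 0.834, 0.795 and 0.699, so the maximum is 0.834 at 6 h. At 24 h, C = c(24) + c(12) = 0.462 + 0.699 = 1.161. Ratio 1.161/0.834 = 1.39.

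All nine scenarios:

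| Half-life, Tmax (h) | First-dose sampled max (6 h) | 24 h sample | Ratio | Modelled peak, time (h) | 24 h / peak | Milk: highest / highest in 0-12 h |
|---|---|---|---|---|---|---|
| 20, 4 | 0.840 | 1.143 | 1.36 | 1.477, 15.4 | 0.77 | 1.61 |
| 20, 5 | 0.834 | 1.161 | 1.39 | 1.439, 16.1 | 0.81 | 1.58 |
| 20, 6 | 0.812 | 1.179 | 1.45 | 1.403, 16.8 | 0.84 | 1.61 |
| 22, 4 | 0.853 | 1.199 | 1.41 | 1.516, 15.4 | 0.79 | 1.63 |
| 22, 5 | 0.847 | 1.215 | 1.43 | 1.480, 16.1 | 0.82 | 1.60 |
| 22, 6 | 0.828 | 1.231 | 1.49 | 1.446, 16.9 | 0.85 | 1.64 |
| 24, 4 | 0.864 | 1.248 | 1.44 | 1.549, 15.4 | 0.81 | 1.65 |
| 24, 5 | 0.859 | 1.263 | 1.47 | 1.515, 16.1 | 0.83 | 1.61 |
| 24, 6 | 0.841 | 1.278 | 1.52 | 1.483, 16.9 | 0.86 | 1.66 |

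- **Plasma.** The 24 h sample is the highest scheduled sample in all nine. A first-dose Cmax would be 1 − 1/1.36 = 26% to 1 − 1/1.52 = 34% below it. The ordering reverses only if the half-life falls below about 10.3 h (Tmax 4 h) or 9.0 h (Tmax 5 h), well under the protocol's 20-24 h.
- **Milk, conditional.** The shortfall is 1 − 1/1.58 = 37% to 1 − 1/1.66 = 40%. The highest collection is 12-18 h in six scenarios and 18-24 h in three.
- **Limit of a whole-profile plasma maximum.** The 24 h sample is 77-86% of the modelled peak and comes 7.1-8.6 h after it, because nothing is sampled between 12 and 24 h.

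**The case against.** The strongest reply is that the SAP already has a definition. Section 5.7.2 says the parameters are defined in Table 3, and a maximum with no stated limit ordinarily means the maximum of the whole profile. The milk list is the only milk-specific instruction, comes later and carries no first-dose limit. The derivation sentence says the parameters will include first-dose values, which does not exclude others. It also lists half-life, which Table 3 defines for plasma only, so the sentence may be meant for plasma alone.

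Most of this stands. A reader might infer that the SAP restricts Cmax and Tmax to the first dose and offers no other definition. The documents do not support that: Table 3 and the closing lists are unrestricted. A reader might also take the 37-40% milk shortfall as the main result. It requires a general sentence to override the milk-specific one, and milk to parallel plasma, and neither is established. The reply does not remove the conflict, because the derivation sentence is still there and a programmer could follow it. Nor is the phrase about total milk concentration data decisive: total may describe the drug measured within a collection, as in the infant-dosage formula in SAP 5.7.1, and not all collections together.

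A second reply is that a first-dose plasma peak is defensible, since it is sampled at 2, 6, 8 and 12 h and the second-dose peak is not sampled. That is a good reason to keep first-dose rows, with a label. It does not make them the regimen's Cmax.

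A third reply is that the consequence is small because the later values appear anyway. SAP 5.7.1 does require concentration summaries by nominal time, individual listings and 0-108 h plots. The table shells are not among the documents, so row labels cannot be checked.

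**Conclusion.** The point holds as an inconsistency within SAP 5.7.2 on the window for two primary endpoints, one side of which conflicts with Protocol 15.4. Confidence is moderate, because the sentence is not exclusive and may be limited to plasma.

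The plasma consequence leads. If the sentence is followed, the 24 h sample, 1.36-1.52 times the first-dose sampled maximum in the model, is shut out of Cmax, and Tmax reads about 6 h when the modelled regimen peak is at 15.4-16.9 h. The milk figure is secondary and conditional. All sizes rest on the one-compartment superposition model, and the ranges reflect only Tmax and half-life, so they understate the real uncertainty.

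A reader might infer that infant exposure would be understated too. It would not be: AUC0-24, Cav (AUC0-24/24), M/P, daily infant dosage and relative infant dose do not use Cmax. SAP 5.7.2 itself names the AUC0-24 milk-to-plasma ratio as of primary interest, and no numerical decision rule depends on Cmax or Tmax.

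**What to change.** Amend SAP 5.7.2 before the interim soft lock:

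1. Reword the derivation sentence to agree with Table 3, the closing lists and Protocol 15.4: Cmax and Tmax are taken over all post-dose plasma samples and all post-dose milk collections, 0-108 h, with Tmax timed from the first dose.
2. Keep first-dose values as separate rows labelled first dose (0-12 h). For plasma this is the better-sampled peak.
3. Footnote the overall plasma rows: no sample is scheduled between 12 and 24 h, so the observed Cmax probably understates the true peak (the 24 h sample is about 77-86% of it in the model), and a Tmax of 24 h may reflect the schedule.

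The cost is a change of wording, one footnote and one extra labelled row for each of Cmax and Tmax. No new samples are needed.

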### **11.3.5. Breast Feeding**

Participants must refrain from all infant breast feeding from prior to dosing on study Day 1 through Day 5 (96 hours after the second dose). Alternative infant nutrition (previously stored breastmilk or infant formula) will be used for feeding the infant during this time period, with acceptance of bottle feeding prior to study start. If a participant discontinues from the trial early for any reason, she must not breast feed her infant until after Day 5 or 96 hours after the second dose of study drug.

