### **13.2. Breast Milk Collection**

Electronic breast pumps will be provided to the participants. Breast milk samples will be collected at time intervals specified in the Schedule of Assessments ([Table 5](#)). The milk should be pumped/expressed completely from both breasts at the time intervals specified. The date, time, and volume of milk expressed will be collected and recorded on the eCRF.

NOTE: No breast milk, after the pumping prior to the Day 1 AM dose through the poststudy visit, should be provided to an infant.

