### Breast Milk PK Sampling Timepoints

PK Sampling Timepoint (measured from Day 1 zero hour)	Tolerance Window
<0 hour	-20 minutes to 0 hour
≥0 hour - 108 hour	-5 minutes to +5 minutes

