4.5.1 Pharmacokinetic Measurements

For pharmacokinetic (PK) assessments, the concentration of ibrexafungerp will be obtained from the blood sample and breast milk sample.

The blood samples will be obtained at the following timepoints: 0 hours (prior to first dose), and at 2, 6, 8, 12 (prior to second dose), 24, 36, 48, 72 and 108 hours post first dose of study drug for determination of ibrexafungerp concentrations in plasma. The 12-hour samples will be taken prior to the second dose of ibrexafungerp.

In breast milk, complete expression of milk from both breasts (using a standard electric breast pump) will be obtained at the following timepoint and intervals: pre-dose, 0-2, 2-4, 4-8, 8-12, 12-18, 18-24, 24-36, 36-48, 48-72, and 72-108 hours post first dose of study drug.

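### SAP 5.7.2 applies a point-sample trapezoid to milk collected over intervals of 2 to 36 h, and neither document says which time represents an interval or whether its milk is pooled

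*SAP*

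**What the plan says.** SAP 4.5.1 and Protocol 15.4 schedule complete milk expression at "pre-dose, 0-2, 2-4, 4-8, 8-12, 12-18, 18-24, 24-36, 36-48, 48-72, and 72-108 hours post first dose of study drug". The ten post-dose intervals are 2, 2, 4, 4, 6, 6, 12, 12, 24 and 36 h wide, and six of them fall within 0-24 h.

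SAP 5.7.2 gives one rule for both matrices: "AUC determination will be based on the linear trapezoidal rule, and actual PK sample times will be used for the PK analyses". SAP Table 3 applies AUC0-24, AUC0-t and AUC0-inf to plasma and breast milk alike, but defines the elimination rate constant and half-life for plasma only. Cav is AUC0-24 divided by 24 h, and M/P is the ratio of the two AUC0-24 values. SAP 5.7.2 names that ratio as being of primary interest.

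Four other places bear on the time of a milk sample:
- SAP 5.7.2 also asks for milk AUC "for the different collection periods", without a formula.
- SAP 5.7.1 lists actual milk and blood sampling dates and times, and volume per interval.
- Protocol 13.2: "The date, time, and volume of milk expressed will be collected and recorded on the eCRF". It does not say whether that time is the start, middle or end of an interval.
- Protocol Appendix A gives milk a tolerance of minus "5 minutes to +5 minutes", a window suited to clock times.

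**The concern.** A linear trapezoid joins concentrations that belong to instants. Milk that accumulates over an interval gives an average, and an average has no sample time until someone assigns one. If it is dated at the interval's end, the milk curve shifts later by half an interval: 1 h for the first collection, 18 h for the last. AUC is then understated while concentrations rise and overstated while they fall. Other dates give other errors.

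Milk AUC and Cav are primary endpoints (SAP 3.1), and milk AUC0-24 is the numerator of M/P. Two analysts following the same SAP on the same data could report different values. The five-participant interim (SAP 5.9) runs the full SAP analysis and may end recruitment, so the rule matters from that point.

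**Working it through.** **The plan's own figure.** Protocol 7.2 supports the 108 h horizon by saying about 15% of drug remains at 72 h with a 24 h half-life. For doses at 0 and 12 h: (2^(-72/24) + 2^(-60/24))/2 = (12.5% + 17.7%)/2 = 15.1%. It reproduces. Protocol 7.1 gives a half-life of about 20 h, so both values are used below.

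**Inputs from the documents.** Half-life 20 or 24 h; single-dose Tmax 4, 5 or 6 h (Protocol 7.1); doses at 0 and 12 h; the milk intervals above; plasma at 0, 2, 6, 8, 12, 24, 36, 48, 72 and 108 h.

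**Assumptions.** One compartment with first-order absorption; milk proportional to plasma (true M/P = 1); constant milk production; each collection equal to its interval mean. The documents contain no milk data.

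**Formulas.** C(t) = f(t) + f(t-12), with f(t) = exp(-ke·t) - exp(-ka·t) for t > 0, ke = ln2/half-life, and ka solving ln(ka/ke)/(ka-ke) = Tmax. The interval mean is the exact integral over the interval divided by its width. The trapezoid runs through these means, with a pre-dose zero for midpoint and end dating. For AUC0-inf, the slope comes from the last three points.

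**One case in full** (half-life 20 h, Tmax 5 h, ka = 0.607/h, arbitrary units). Interval means: 0.387, 0.730, 0.780, 0.705, 1.231, 1.210, 0.896, 0.591, 0.324, 0.119.
- Exact AUC, which equals the sum of mean × width: 22.82 (0-24 h) and 52.70 (0-108 h).
- End-dated trapezoid, 0-24 h: 0.387 + 1.117 + 3.019 + 2.969 + 5.808 + 7.324 = 20.62; 20.62/22.82 = 0.904, or -9.6%.
- End-dated trapezoid, 0-108 h: 20.62 + 12.64 + 8.92 + 10.98 + 7.96 = 61.12; 61.12/52.70 = 1.160, or +16.0%.

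**All six half-life and Tmax combinations, error against true milk AUC:**

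| Time given to interval milk | AUC0-24 and Cav | AUC to last time vs true 0-108 h | AUC0-inf |
|---|---|---|---|
| End (last time 108 h) | -9.0% to -10.5% | +14.4% to +16.0% | +20% to +21% |
| Midpoint (last time 90 h) | -2.6% to -2.9% | -1.4% to -3.0% | about +2% |
| Start (last time 72 h) | +0.5% to +2.9% | -18.7% to -20.4% | -16% to -17% |
| Mean × width, summed | 0 | 0 | not applicable |

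The dating choice moves AUC0-24 by up to about 13 percentage points. The extrapolated share is 5.8% to 10.6% throughout, so the SAP's 20% exclusion is not triggered.

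**Single-expression reading.** If each collection is one expression equal to plasma at interval end, the trapezoid error is -6.4% to -8.7% (0-24 h) and -0.3% to -1.5% (0-108 h). On such data, mean × width would be the wrong tool: it understates AUC0-108 by about 15%.

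**Effect on M/P.** Plasma has no sample between 12 and 24 h, so its trapezoid misses the second-dose peak and understates AUC0-24 by 18% to 21%. In the case above the plasma ratio is 0.804. M/P over 0-24 h is then 0.904/0.804 = 1.12 with end-dated milk and 1/0.804 = 1.24 with exact milk. Over all six cases the overstatement is 9% to 15% with end-dated milk and 22% to 26% with exact milk. Over 0-108 h the plasma error is only about -5% to -7%.

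**The case against.** The strongest reply is that the SAP never dates milk at the interval end. That is right: the defect is an undefined convention, and the larger errors are conditional. Midpoint dating nearly removes the AUC bias. The clock-time tolerance and recorded expression times also allow the single-expression reading, under which the 0-108 h error almost vanishes. An error of 6% to 9% in AUC0-24 remains even then, and nothing in the text selects either reading.

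The plan also already names milk AUC per collection period, which is the right quantity. This stands too, but without a formula the trapezoid is the only rule to apply.

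A reader might infer more than the documents support:
- **That no milk value exists at 108 h.** End dating places one there, and SAP 5.7.2 proceeds "since blood samples and breast milk will be collected to 108 hours". Pooled 72-108 h milk would be an average, but no passage makes a planned decision depend on a spot milk value at 108 h; the breastfeeding restriction is a fixed period. A separate 108 h aliquot is not called for on this ground.
- **That the rule seriously delays milk Tmax.** SAP 5.7.2 specifies Tmax after the first dose. End dating gives 4-8 h against a true 4-6 h. The coarseness comes from interval width, which no AUC rule removes.
- **That a reported milk half-life would be wrong.** Table 3 plans half-life for plasma only. The slope matters in milk only through AUC0-inf.
- **That infant exposure is biased.** Daily infant dosage sums concentration × volume and uses no trapezoid; relative infant dose follows from it.

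**Conclusion.** The point holds as a missing definition with a material, conditional effect. For pooled interval milk, the choice of date moves milk AUC0-24 and Cav from about -10.5% to about +3%. End dating overstates AUC0-108 by 14% to 16% and AUC0-inf by about 20%. For single equilibrated expressions, the errors are -6% to -9% over 0-24 h and at most 1.5% over 0-108 h. These sizes rest on the one-compartment model, a constant M/P and constant milk production.

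Concentration × interval duration is exact under the pooled assumptions and should replace the trapezoid for milk, provided the assayed milk represents the whole interval. It does not repair M/P over 0-24 h: in this model, end-dated milk partly offsets the plasma error, and correcting milk alone exposes that error in full.

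**What to change.** In SAP 5.7.2, for milk only:

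1. State that all milk expressed in an interval is pooled, or its assays volume-weighted, into one concentration.
2. Define AUC for each collection period as that concentration × actual interval duration, from the end of the previous complete expression to the end of the current one.
3. Sum the periods for AUC0-24 and AUC0-t, and derive Cav from the AUC0-24 sum.
4. Use interval midpoints for plots and for any terminal slope behind milk AUC0-inf, and say how that slope is fitted.
5. Report milk Tmax as an interval.

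For M/P, state that plasma AUC0-24 has no sample between 12 and 24 h and do not present M/P over 0-24 h as corrected by the milk change. Also report M/P on AUC0-t (0-108 h), where the modelled plasma error is about 5% to 7%.

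The cost is one SAP paragraph and a little more analysis work, with no added visits or samples. It should be settled before the five-participant interim analysis.

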5.8 Safety Analysis

The safety and tolerability of ibrexafungerp will be assessed by the evaluation of adverse events, vital signs (blood pressure, heart rate, respiratory rate, and temperature), physical examination, 12-lead electrocardiogram (ECG), and laboratory safety (biochemistry, hematology, coagulation and urinalysis).

Safety variables will be listed by all participants in the Safety Population.

